STUDY PROTOCOL AND STATISTICAL ANALYSIS PLAN

Title:

Comparative Effects of High-Intensity Interval Training Modalities on Physical Performance and Physiological Responses in Competitive Table Tennis Players

Brief Title:

HIIT Effects on Table Tennis Players

Unique Protocol ID:

E-77192459-050.99-376986

ClinicalTrials.gov Identifier:

NCT Number: Not yet assigned

Document Type:

Study Protocol and Statistical Analysis Plan

Sponsor:

Karabük University

Principal Investigator:

[name] [name]

Ethics Approval:

Karabük University Non-Interventional Clinical Research Ethics Committee

Decision No: 2024/1956

Approval Number: E-77192459-050.99-376986

Approval Date: 27 September 2024

Document Date:

03 January 2026

Study Objectives

To examine the comparative effects of calisthenic/plyometric HIIT and kettlebell-based Tabata HIIT on physical performance and physiological responses in competitive table tennis players.

Study Design

Randomized, parallel-group experimental study conducted over 8 weeks.

Participants

- Sample size: 24 male competitive table tennis players
- Age range: 18–24 years
- Inclusion criteria: actively training competitive athletes
- Exclusion criteria: musculoskeletal injury, cardiovascular or metabolic disease

Interventions

Group 1 – Calisthenic/Plyometric HIIT

- Tabata-based HIIT protocol
- 3 sessions/week for 8 weeks
- Performed in addition to regular table tennis training

Group 2 – Kettlebell HIIT

- Tabata-based HIIT protocol
- 3 sessions/week for 8 weeks
- Performed in addition to regular table tennis training

Outcome Measures

Primary Outcomes:

- Agility
- Flexibility
- Vertical jump
- VO₂max

Secondary Outcomes:

- Sprint performance
- Peak power
- Average power

Data Collection

Outcome measures assessed at baseline (pre-intervention) and post-intervention (8 weeks).

Statistical Analysis Plan

- Software: SPSS and/or R
- Analysis population: Intention-to-treat
- Descriptive statistics: Mean \pm standard deviation
- Inferential analysis

2 \times 2 mixed-design ANOVA

Within-subject factor: time (pre vs post)

Between-subject factor: group

Post-hoc paired-sample t-tests with Bonferroni correction

Statistical significance: $p < 0.05$

Confidentiality

All participant data are anonymized. No identifying information is included in this document.

INFORMED CONSENT FORM

Title:

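### The 2x2 mixed ANOVA is a valid but usually less precise way to compare the two randomized modalities than an ANCOVA on the baseline already collected, and the planned paired t-tests do not estimate the difference

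*Protocol*

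**What the plan says.** The Study Objectives section sets a single, comparative aim: "To examine the comparative effects of calisthenic/plyometric HIIT and kettlebell-based Tabata HIIT" on performance and physiological responses. The Study Design section describes a "Randomized, parallel-group experimental study conducted over 8 weeks", and the Participants section gives "Sample size: 24 male competitive table tennis players". Under Data Collection, each outcome has one baseline value and one value at 8 weeks. The Outcome Measures section lists four primary and three secondary outcomes.

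The Statistical Analysis Plan section fixes a 2x2 "mixed-design ANOVA" with time (pre, post) as the within-subject factor and "Between-subject factor: group". The only follow-up it names is "Post-hoc paired-sample t-tests with Bonferroni correction". Baseline therefore enters as one of the two response levels and not as a covariate. The section names no between-group estimate and no confidence interval.

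**The concern.** In a randomized trial with one pre and one post measurement, the question is how far the post values differ between arms, given where the players started. The mixed ANOVA answers it through group-by-time, which subtracts the whole baseline from the post value. Where pre and post are only moderately correlated, that subtraction adds noise. It also carries any chance baseline difference between the arms into the estimated modality effect. ANCOVA estimates the weight on baseline from the data and avoids both.

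Paired t-tests in two independent arms can only compare pre with post within an arm. As the only named follow-up, they direct the report to whether each programme is associated with change, which is not the stated objective. With 24 players, precision that costs no new data is worth having.

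**Working it through.** The document states no power, SD, effect size or pre-post correlation, so there is no figure of its own to reproduce.

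**Inputs from the document:** 24 players, two arms, one pre and one post value, seven outcomes (4 + 3), significance level 0.05.

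**Assumptions:** 12 per arm, two-sided testing, bivariate normal data, pre and post SD both 1, post difference of 1 SD, and correlation ρ varied.

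**Step 1: what the planned test is.** With two time points, the group-by-time F equals the squared two-sample t on change scores. A numerical check gave F = t² = 3.3603. The group main effect averages pre and post, so its expected value is (0 + δ)/2, half the true post difference δ. Group-by-time is therefore the relevant term.

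**Step 2: variances**, with n per arm:

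- Group-by-time: 2(1 − ρ) × 2/n
- ANCOVA: (1 − ρ²) × 2/n, times about 1 + 1/(N − 4) = 1 + 1/20 = 1.05 for estimating the slope at N = 24
- Ratio, ANCOVA to group-by-time: (1 + ρ)/2 × 1.05

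At ρ = 0.5 the ratio is 0.75 × 1.05 = 0.79. It equals 1 at ρ = 2/1.05 − 1 = 0.905. At ρ = 0.95 it is 0.975 × 1.05 = 1.024.

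**Step 3: power and interval width** (200,000 simulated trials per cell):

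| ρ | Variance ratio | Power, ANCOVA | Power, group-by-time | Mean 95% CI half-width, ANCOVA v group-by-time (SD) |
|---|---|---|---|---|
| 0.3 | 0.68 | 67% | 51% | 0.82 v 0.99 |
| 0.5 | 0.79 | 75% | 65% | 0.74 v 0.84 |
| 0.7 | 0.89 | 89% | 86% | 0.61 v 0.65 |
| 0.8 | 0.95 | 97% | 96% | 0.52 v 0.53 |
| 0.9 | 1.00 | >99% | >99% | 0.37 v 0.37 |

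Type I error was 4.9 to 5.1% for both tests at every ρ. To match ANCOVA with 12 per arm, group-by-time needs 15, 14, 13 and 12 per arm at ρ = 0.5, 0.7, 0.8 and 0.9.

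**Step 4: sensitivity.** For a 0.5 SD difference, power is 26 v 22% at ρ = 0.5 and 36 v 33% at 0.7. A 10:14 split with a 1 SD difference gives 74 v 64% and 88 v 85%.

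**Step 5: chance baseline imbalance.** With 12 per arm, the SD of the baseline difference is √(2/12) = 0.41 SD per outcome. The group-by-time estimate shifts by (1 − ρ) times that difference, in the opposite direction: 0.5 × 0.41 = 0.20, 0.3 × 0.41 = 0.12 and 0.1 × 0.41 = 0.04 SD at ρ = 0.5, 0.7 and 0.9. In simulation the ANCOVA estimate moved by no more than 0.002 SD.

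A difference beyond 0.8 SD (0.8/0.408 = 1.96 standard errors) arises in 5% of randomizations per outcome. For at least one of seven outcomes the chance is 1 − 0.95⁷ = 30% if they are independent, and less if correlated. With the imbalance fixed at 0.8 SD, the conditional type I error of group-by-time is 12, 9 and 6% at ρ = 0.5, 0.7 and 0.9, against 5% for ANCOVA.

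**The case against.** The strongest reply is that nothing here is wrong. Group-by-time is unbiased under randomization, holds 5% error and tests the stated objective. The paired tests are labelled post hoc, and the plan states no rule that compares modalities by within-arm p-values. All of this stands, and no error rate is claimed against the paired tests.

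The size of the gain also depends on inputs that the document does not give. Correlations near 0.9 are plausible for highly repeatable performance tests, and there the gain vanishes. At a 0.5 SD difference neither analysis has adequate power.

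The break-even depends on equal SDs. If the post SD is 1.1 times the pre SD, the variance ratio is 1.21(1 − ρ²) × 1.05 / (2.21 − 2.2ρ). This gives 0.97, 1.02 and 1.05 at ρ = 0.7, 0.8 and 0.9, so break-even falls to about 0.77. A smaller post SD favours ANCOVA.

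The conditional error also runs both ways. At zero imbalance group-by-time is conservative (about 2.6, 3.4 and 4.5% at ρ = 0.5, 0.7 and 0.9), and at a 0.41 SD imbalance it is close to 5%.

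These points limit the concern but do not remove it. ANCOVA's possible loss is small: when the true slope is exactly 1, the change score is already optimal, and ANCOVA pays only the slope-estimation factor of 1.05, about 5% in variance. Its possible gain is much larger: 32% lower variance at ρ = 0.3 and 21% at 0.5.

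**Conclusion.** The point holds, as a minor one. The planned analysis is valid, but it is usually less precise than a baseline-adjusted analysis of the same two measurements, and its only named follow-up does not estimate the quantity in the objective. Under the stated assumptions the gain is about 10 percentage points of power at correlation 0.5, 3 at 0.7, 1 at 0.8 and none at 0.9. Above about 0.905 ANCOVA is marginally worse. That break-even assumes equal pre and post SDs and falls if the post SD is larger. The benefit lies in precision and in protection against the imbalance that actually occurs, not in average type I error. The reporting part of the point does not depend on the correlation.

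**What to change.** In the Statistical Analysis Plan section, specify for each outcome an ANCOVA of the 8-week value on group, adjusted for that outcome's baseline. Report the adjusted difference between modalities with its 95% CI. If the mixed ANOVA is kept, an acceptable alternative is to name group-by-time as the deciding term and report the difference in mean change with its 95% CI. In either case, present pre-post changes per arm as descriptive means with CIs, and draw no claim about one modality against the other from within-arm p-values.

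The change is to wording only. It needs no new data, and the software already named can fit the model. ANCOVA uses one more degree of freedom (21 residual against 22) and assumes a linear baseline slope common to both arms.

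### The aim is to compare two HIIT modalities, but no model term is tied to it and the only follow-ups fixed are paired t-tests, which cannot compare the arms: make the baseline-adjusted between-group difference at 8 weeks the deciding test

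*Protocol*

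**What the plan says.** The Study Objectives section states the aim as "To examine the comparative effects of calisthenic/plyometric HIIT and kettlebell-based Tabata HIIT" on performance and physiological responses. The Study Design section describes a "Randomized, parallel-group experimental study conducted over 8 weeks", and the Participants section gives "Sample size: 24 male competitive table tennis players". Both arms receive an active HIIT programme on top of their usual table tennis training. All outcomes are measured twice, before the intervention and at 8 weeks.

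Under Inferential analysis, the Statistical Analysis Plan section fixes a 2 × 2 mixed-design ANOVA. Time (pre, post) is the within-subject factor, and the other is given as "Between-subject factor: group". The only follow-up is "Post-hoc paired-sample t-tests with Bonferroni correction", with significance at p < 0.05. The section does not name an ANOVA term as the test of the objective, a condition for running the paired tests, or a between-group estimate or interval.

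**The concern.** In a parallel-group trial the pairing is within a player, so a paired t-test compares that player's 8-week value with his baseline. Done by arm, it asks whether that arm changed. Pooled over arms, it asks whether players changed on average. Neither asks whether one modality does better than the other.

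The paired tests are valid for change within an arm. The difficulty is that they are the only follow-ups fixed and the text attaches no condition to them. A report could therefore say that one modality improved an outcome significantly and the other did not, and present this as the comparative finding. A difference between two p-values is not a test of a difference. At this sample size the pattern arises readily when the modalities are equally effective. Both arms train actively, so a shared gain is plausible.

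Leaving the ANOVA term unnamed adds a smaller risk. The group main effect averages the pre and post values, so it is a poor test of the comparison if someone reads it as the answer.

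**Working it through.** **Inputs.** From the protocol: 24 players, two parallel arms, two time points, seven outcomes (four primary, three secondary), alpha 0.05. Not in the protocol and therefore assumed: 12 per arm, two-sided tests, normally distributed changes, and the pre–post correlations and effect sizes shown below. The protocol gives no figure on this point to reproduce.

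**Step 1: how often only one arm is significant when the arms do not differ.** Let both arms share a true change of d SDs of the change score. The power p of one paired test comes from the noncentral t with 11 degrees of freedom and noncentrality d√12. The arms are independent, so P(exactly one significant) = 2p(1 − p). Example at d = 0.8 and alpha 0.025 (Bonferroni over two arms): p = 0.584, and 2 × 0.584 × 0.416 = 0.486.

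| Shared change d | 0.2 | 0.5 | 0.8 | 1.0 | 1.2 | 1.5 |
|---|---|---|---|---|---|---|
| p, alpha 0.025 | 0.054 | 0.241 | 0.584 | 0.793 | 0.922 | 0.990 |
| Exactly one arm, no gate | 10% | 37% | 49% | 33% | 14% | 2% |
| Same, and time effect p < 0.05 | 7% | 34% | 48% | 33% | 14% | 2% |
| Same, and interaction p < 0.05 | 3% | 4% | 4% | 3% | 2% | 0.4% |
| Exactly one arm, no gate, alpha 0.05/14 | 2% | 13% | 38% | 50% | 44% | 19% |

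The two gated rows come from simulation (400,000 trials per value of d). The protocol does not say how many tests the Bonferroni correction covers, so the last row takes 7 outcomes × 2 arms = 14. That moves the peak to larger gains but does not remove it. The interaction test itself rejects in 5% of trials throughout. A gate on the time effect hardly helps from d = 0.5 upwards; a gate on the interaction does.

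**Step 2: the cost of reading the wrong ANOVA term.** For a true between-arm difference of 0.8 outcome SD, simulated power at correlation r = 0.5, 0.7 and 0.9 is:

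- group main effect: 19%, 17%, 16%
- group-by-time interaction: 46%, 68%, 99%
- ANCOVA: 55%, 73%, 99%

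**Step 3: interaction against ANCOVA.** With two groups and two times, the interaction is the same as a two-sample t-test on change, with variance proportional to 2(1 − r). ANCOVA of the 8-week value on group and baseline has variance proportional to 1 − r². The large-sample ratio is (1 − r²)/[2(1 − r)] = (1 + r)/2. Simulation (40,000 trials each, equal variances) shows what is left of this at 12 per arm:

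| r | 0.3 | 0.5 | 0.7 | 0.9 |
|---|---|---|---|---|
| Variance ratio, large sample | 0.65 | 0.75 | 0.85 | 0.95 |
| Variance ratio, 12 per arm | 0.68 | 0.79 | 0.89 | 1.00 |
| Mean 95% CI half-width, ANCOVA (outcome SD) | 0.819 | 0.745 | 0.613 | 0.375 |
| Mean 95% CI half-width, change score (outcome SD) | 0.990 | 0.837 | 0.648 | 0.374 |
| Power for 0.5 SD, ANCOVA | 22% | 26% | 36% | 75% |
| Power for 0.5 SD, change score | 17% | 22% | 33% | 75% |
| Verdicts differ at 0.5 SD | 15% | 14% | 13% | 7% |

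Type I error is 0.049–0.051 for both methods.

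**The case against.** The strongest reply is that the plan already holds a valid test. The group-by-time term is the between-arm contrast of change, has one degree of freedom and keeps its 5% error, so no between-group follow-up is needed. This stands, and the concern is not that a comparison is absent. What is missing is a commitment to that term.

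Second, the tests are called post-hoc and follow the ANOVA, so a sympathetic reader would run them only after a significant interaction. On that reading the one-arm-only pattern falls to 0.4–4% and the problem is small. The text does not state this condition, however. A gate on the time effect fits the wording equally well and leaves the figures almost unchanged.

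Third, nothing in the protocol says the arms will be compared by their paired p-values. This is true; the charge is that the text permits it.

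Fourth, ANCOVA is partly a preference. Both methods are valid, the gain depends on an assumed correlation, and it vanishes near r = 0.9. Naming the interaction would be the minimum repair. ANCOVA is still the better choice, because it uses a baseline already collected and is more precise over much of the plausible range.

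Fifth, one deciding test for each of four primary outcomes leaves the family-wise error at up to 1 − 0.95⁴ = 18.5% if the tests are independent. This is correct, but it is a separate matter from which contrast is tested.

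Detail of this kind is often left to a separate analysis plan. Here the document calls itself both protocol and statistical analysis plan and fixes this analysis itself.

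**Conclusion.** The concern holds. The objective is comparative, no ANOVA term is tied to it, and the only follow-ups fixed cannot compare the modalities. If the arms are compared by separate paired results, two equally effective modalities look different in about a third to a half of trials for shared gains of 0.5 to 1.0 SD of change at alpha 0.025. The figure is much lower for very small or large gains, and at most 4% under an interaction gate. These figures rest on 12 per arm, normal changes and the assumed gain; they do not depend on the pre–post correlation. The ANCOVA gain does depend on it: the interval is about 17% narrower at r = 0.3 (0.819 against 0.990), 11% at 0.5, 5% at 0.7, and no narrower at 0.9. The plan should be changed, but a valid test is already within it, so the defect is not fatal.

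**What to change.** In the Inferential analysis part of the Statistical Analysis Plan section, before outcome data are examined:

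- State that, for each outcome, the test of the objective is the between-group difference at 8 weeks from an ANCOVA of the 8-week value on group and baseline value, reported with its 95% CI.
- Keep the group-by-time interaction from the mixed ANOVA as a supportive analysis. The two methods can reach different verdicts, so their order must be fixed in advance.
- Report within-arm changes as supportive (mean change with 95% CI), and state that the arms are not compared by their separate paired p-values.

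The cost is wording only, since both measurements are already collected. ANCOVA uses one degree of freedom and gains nothing when r is near 0.9. The comparison may well be inconclusive: the unadjusted contrast has a half-width of t(0.975, 22) × √(2/12) = 2.074 × 0.408 = 0.85 SD of change at 12 per arm. That is a limit of the sample size, and the interval will show it openly. A multiplicity rule for the between-group tests on the four primary outcomes still has to be set separately, because the stated Bonferroni correction is attached only to the paired tests.
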